### Inclusion Criteria:

- Male or female age 18-75 years
- $BMI \geq 27.0 \text{ kg/m}^2$  to  $\leq 47.5 \text{ kg/m}^2$
- Completed genealogy test by a company, such as Ancestry, 23andMe or GeneticDirection that allows customers to download the raw data files. Willing to provide the research team with the raw genealogy data. Has a genetic profile indicating the predisposition to respond favorably to either a high-carbohydrate or high-fat weight loss diet. We estimated that approximately 1/3 of people are fat responders, 1/3 are carbohydrate responders, and 1/3 are neither or will respond to either diet. Only carbohydrate and fat responders are eligible.
  - It is unclear what percentage of the Baton Rouge population has genealogy data. Thus, the budget will include funds (\$125/each) to pay for genealogy testing.

### Exclusion Criteria:

- Current smoker or has smoked in the previous year

- For females, pregnant or planned pregnancy during the study duration, or breast-feeding, based on self-report
- Conditions, diseases, or medications that affect body weight or metabolism (e.g., certain antipsychotic medications; type 2 diabetes mellitus; heart failure; cancer, excluding certain melanomas; etc.)
- Has gained or lost more than 10 pounds in the last 3 months
- Currently diagnosed with an eating disorder, major depression, or other condition that, in the judgment of the investigators, could affect risk to the participant or study completion

### **Power analysis**

This study will plan to obtain data on up to 154 participants in total. During a previous 12-week study that had a similar weight loss strategy, participants lost 5.1 kg with an SD of 3.3 kg. This SD is larger than the SD for between-group differences observed in other studies conducted by the PBRC group, which range from 2.1 to 2.8 kg; therefore, an SD for between-group differences in weight change of 2.8 kg was utilized. The power analysis for the proposed study uses a T-test to determine differences and assumes an alpha level of 0.05 and power  $\geq 0.80$  as acceptable. Weight loss in cells A and D are both expected to be similar in the previous study while the weight loss in cells B and C would have similar but approximately half that effect of the previous study. To detect a 2.0 kg difference in weight change between either A vs. B or C vs. D, this study would have a power of 0.80. A 2.0 kg difference is approximately 2.2% of body weight assuming the mean body mass of participants is 90 kg. Based on the assumptions above, this study has power over 0.95 to test if the diet that corresponded to their genotype lost more weight than those assigned to a diet inconsistent with their genotype.

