- **Hypothesis 2b:** Carbohydrate responders will lose more weight on the high-carbohydrate diet vs. the high-fat diet.

Carbohydrate and dietary fat responders will be identified *a priori* based on their combined genotypes at pre-determined genetic variants using specific algorithms. Carbohydrate responders and fat responders will be randomized to one of the following two diets:

1. A high-quality high-carbohydrate diet that is rich in whole-grain foods, or
2. A high-quality high-fat diet that is rich in unsaturated fats and oils (Table 1).

**Table 1.** Overview of the study design and expected relative weight loss (double arrows reflect greater expected weight loss). The total number per group is an estimate. We will not close cells to enroll this exact number per group, and the total number of people enrolled will not exceed 154.

	High-Fat Diet	High-Carb Diet
Fat Responder	Cell A n=52 ↓↓	Cell B n=52 ↓
Carb Responder	Cell C n=25 ↓	Cell D n=25 ↓↓

Both diets will last 12 weeks and have the same levels of protein (15% of energy). The high-carbohydrate diet will consist of ~20% of energy from fat and ~65% from carbohydrates. The high-fat diet will consist of ~40% energy from fat and ~45% from carbohydrates. All participants will be assigned an energy intake target that will result in a daily deficit of ~750 kcal, though no energy intake targets below 1,100 kcal/d (women) and 1,300 kcal/day (men) will be prescribed. At the discretion of the PI or MI, modest diet modifications will be allowed if needed for participant safety. Baseline energy requirements will be calculated with the formulas of Mifflin St. Jeor. The Remote Food Photography Method (RFPM) and SmartIntake smartphone app will be used sporadically as needed to facilitate dietary adherence. These are process data and will not be immediately analyzed to quantify dietary intake, though the images can be fully analyzed later. Rather, the food images will be reviewed by the interventionists in near real-time to help the participant select and eat foods consistent with their meal plan.

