### **Data analytic plan**

The biostatistics department will handle the randomization and use adaptive randomization to promote equal numbers of men and women in each cell and to promote similar BMI across the groups.

The primary outcome variable is body weight change, represented as kg and percent change. All other variables are secondary and will be analyzed using a similar statistical approach. Repeated mixed linear models will be used to determine if change in the outcome variables differs among the groups. Covariates will include the baseline value of the outcome, sex, and race. Additional variable selection in the models will be determined through model fit statistics such as AIC.

Two sources of body weight data are obtained – weights collected in the clinic at baseline and week 12, and weights collected at the 12 intervention sessions. Both sources of data will be analyzed, though the presence of only two clinic weights means that analysis of the clinic weights will be a completers' analysis. The weekly weight data, however, will be analyzed using an intent-to-treat approach, and all participants' data will be analyzed who have a weight from their first and at least one subsequent intervention visit. Sensitivity analysis will be conducted to determine how the two methods effects the results.

The primary models will be a mixed effect model that accounts for the correlation of the subject over time modeling. Least square means based on the estimates from the mixed effect model will be used to test for differences of weight change between groups. Normality of the responses will be checked based on the Shapiro-Wilk test. Heterogeneity of variance effects for genders for each of the treatments will be analyzed first as potential subgroups.

Hypothesis 1 will test if participants assigned to the diet that corresponded to their genotype lost more weight than those assigned to a diet inconsistent with their genotype.

- H1: Weight loss in Cells A and D (combined) in Table 1 was significantly larger than weight loss in Cells B and C (combined).

Hypothesis 2 will analyze the fat responders and carbohydrate responders separately.

- H2a: Fat responders lost more weight on the high-fat diet (Table 1, Cell A) vs. the high-carbohydrate diet (Cell B), and
- H2b: Carbohydrate responders lost more weight on the high-carbohydrate diet (Table 1, Cell D) vs. the high-fat diet (Cell C).

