## Withdrawal of Subjects

Subjects may be withdrawn from the study if he/she misses study visits and will be notified of their withdrawal via telephone or mail. If a subject voluntarily withdraws from the study, no additional data will be collected and they will be considered dropouts in the study.

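### The stated 0.80 power for Cell C vs Cell D at 2.0 kg holds only with a one-sided test and all 25 planned participants per cell analysed; the plan leaves no margin for attrition

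*Combined protocol and SAP*

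**What the plan says.** The Power analysis section "uses a T-test to determine differences and assumes an alpha level of 0.05" and treats power of at least 0.80 as acceptable. For the standard deviation, "an SD for between-group differences in weight change of 2.8 kg was utilized". It then gives a figure of 0.80 in the sentence that begins "To detect a 2.0 kg difference in weight change between either A vs. B or C vs. D, this study would have a power of". It does not say whether the test is one- or two-sided, and it gives no dropout rate. It plans for data on up to 154 people.

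Table 1 (Background) plans 52, 52, 25 and 25 participants in Cells A to D. Its legend calls these estimates and adds: "We will not close cells to enroll this exact number per group, and the total number of people enrolled will not exceed 154".

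On who is analysed, the Data analytic plan says that "the presence of only two clinic weights means that analysis of the clinic weights will be a completers' analysis". The weekly session weights are to be analysed by intent-to-treat, in everyone with a weight at the first session and at least one later session. Under Withdrawal of Subjects, when someone leaves voluntarily, "no additional data will be collected and they will be considered dropouts in the study".

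C vs D is Hypothesis 2b: "Carbohydrate responders will lose more weight on the high-carbohydrate diet vs. the high-fat diet". It is one of the a priori comparisons on the primary outcome, each at alpha 0.05.

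**The concern.** The number enrolled and the number analysed are treated as the same. The cap on enrolment, the number with data in the power section and the sum of the Table 1 cells are all 154. Yet the plan foresees dropouts and defines one of its two weight analyses on completers. A power figure worked out at 25 per cell therefore describes a trial with no loss.

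Only C vs D is exposed, because it is the smallest comparison and the single figure of 0.80 is quoted for it and for A vs B alike. If C vs D shows no clear difference, readers will judge that result against a claimed 0.80 to detect 2.0 kg. If the real figure is nearer 0.7, or 0.6 on a two-sided test, the result says less about Hypothesis 2b than the protocol implies.

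**Working it through.** **Inputs.** Difference 2.0 kg, SD 2.8 kg, alpha 0.05, t-test (Power analysis); 25 per cell for C and D, 52 for A and B (Table 1); cap 154 (Table 1 legend). Attrition is not given, so 10% and 20% are assumptions. The 2.8 kg is used as the common SD of individual weight change, the reading under which the stated 0.80 can be reproduced.

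**Formula.** For n per cell, df = 2n − 2 and the noncentrality is δ / (SD × √(2/n)). Power is the probability that a noncentral t with that noncentrality exceeds the critical value: the 95th percentile of t one-sided, the 97.5th two-sided (plus the negligible opposite tail).

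**Step 1: reproduce the stated figure.** At n = 25 the noncentrality is 2.0 / (2.8 × √(2/25)) = 2.525, with df = 48.
- One-sided, critical value 1.677: power 0.801. This matches 0.80.
- Two-sided, critical value 2.011: power 0.697. This does not.

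The smallest n per cell that reaches 0.80 is 25 one-sided and 32 two-sided. The planned 25 is thus exactly the one-sided minimum.

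**Step 2: margin for loss.** 52 + 52 + 25 + 25 = 154, the cap. At full enrolment there is no allowance.

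**Step 3: C vs D at 2.0 kg with fewer analysed.** A 10% loss leaves 25 × 0.9 = 22.5, taken as 22; a 20% loss leaves 25 × 0.8 = 20.

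| Analysed per cell | One-sided | Two-sided |
|---|---|---|
| 25 | 0.801 | 0.697 |
| 24 | 0.786 | 0.678 |
| 22 | 0.754 | 0.639 |
| 20 | 0.717 | 0.595 |

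**Step 4: difference detectable with power 0.80.** At 25 per cell it is 2.00 kg one-sided and 2.26 kg two-sided. At 20 per cell it is 2.24 kg and 2.55 kg.

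**Step 5: the other comparisons at 2.0 kg.**
- A vs B, 52 per cell: 0.976 one-sided, 0.950 two-sided. After 20% loss (52 × 0.8 ≈ 42): 0.945 and 0.90.
- Hypothesis 1, 77 per group (52 + 25): 0.997 and 0.993. After 20% loss (77 × 0.8 ≈ 62): 0.99 and 0.98, still above the stated 0.95.

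**Step 6: the plan's own expected effect.** The Power analysis section expects Cells A and D to resemble the previous study (5.1 kg) and B and C to lose about half that, a difference of 5.1 − 2.55 = 2.55 kg. At 2.55 kg, SD 2.8 and 20 per cell, C vs D power is 0.882 one-sided and 0.801 two-sided.

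**The case against.** The strongest reply is that the trial remains adequately powered for what it expects to see. At about 2.55 kg, 20 completers per cell still give 0.80 or more on either reading. This stands, so the point is confined to the 2.0 kg claim. It does depend on SD 2.8: with the previous study's 3.3 kg, the same case gives 0.775 one-sided and 0.663 two-sided. In the other direction, 2.8 is the top of the cited 2.1 to 2.8 range, and at 2.1 kg even 2.0 kg has 0.905 one-sided with 20 per cell.

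Second, completers are not the only analysis set. The weekly-weight mixed model keeps people who leave after a second session weight, and the models adjust for baseline value, sex and race. Both should reduce the loss. This stands too, but the documents give neither the within-person correlation nor the variance explained, so the gain cannot be sized. The plan's power statement, a plain t-test, takes no credit for it.

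Three stronger readings are tempting and should be resisted.
- A reader might infer that a single dropout per cell breaks the claim. It moves one-sided power from 0.801 to 0.786, which is immaterial; the loss matters only at around 10 to 20%.
- A reader might infer a rule against replacing dropouts. No such rule is written. The cap prevents replacement only once 154 have been enrolled.
- A reader might infer that completion by exactly 50 carbohydrate responders would secure 0.80. Cell sizes are estimates and cells are not closed, so the number may be higher or lower. If the test is two-sided, 50 completers give only 0.70.

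**Conclusion.** The 0.80 for C vs D at 2.0 kg is wrong as written unless the test is one-sided and 25 per cell are analysed. Neither condition is stated, and the plan's own rules on completers and withdrawal make the second unlikely for the clinic weights. With an assumed 10 to 20% loss the figure is about 0.75 to 0.72 one-sided; two-sided it starts at 0.70 and falls to 0.64 to 0.60. Of the two gaps, undeclared sidedness is the larger: it costs about 0.10 before anyone leaves, against 0.05 to 0.08 for the assumed attrition.

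These sizes rest on SD 2.8, equal cells of the planned size, an unadjusted t-test and an attrition range that the documents do not supply. They apply directly to the clinic-weight analysis and overstate the loss for the weekly-weight model. The documents do not support the conclusion that the trial is underpowered overall, or that C vs D is underpowered for the difference the plan expects.

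**What to change.** In the Power analysis section:

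1. State whether the comparisons are one- or two-sided, and use the same choice in the Data analytic plan.
2. State an assumed 12-week attrition and its basis.
3. Give C vs D power at 2.0 kg, and the difference detectable with 0.80 power, at the expected number of completers. At 20 per cell these are 0.72 and 2.24 kg one-sided, or 0.60 and 2.55 kg two-sided.
4. Keep the claim of at least 0.80 at 2.0 kg for A vs B only.
5. Add that at the expected difference of about 2.55 kg and SD 2.8, C vs D with 20 per cell has about 0.88 (one-sided) or 0.80 (two-sided).
6. Say that these figures describe the completers' analysis, and that the weekly-weight model is expected to lose less.

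The cost is protocol wording. Enrolment, the cap and the analyses stay as they are. The one disadvantage is a less favourable stated figure for Hypothesis 2b.

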The *a priori* comparisons noted above will rely on an alpha level of 0.05 for both measures of body weight (kg and %). In addition, we will conduct tests with alpha equal to 0.05 to determine if baseline insulin levels and HOMA (homeostatic model assessment) are associated with weight loss and differential weight loss between the groups and diets. Alpha will be adjusted in the analyses of all other variables using the family-wise error rate employing the Holm-Bonferroni method, which is based on the number of p-values less than alpha.

The Report to the sponsor will include data tables for all outcome variables at all assessment visits, as well as tables depicting change on the outcome variables and the associated inferential statistics. Tables depicting participant demographics will also be provided.

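### One power figure, 0.80 at 2.0 kg, is given for both A vs. B and C vs. D, but at the planned cell sizes it understates A vs. B and fits C vs. D only if the test is one-sided, which the plan does not say

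*Combined protocol and SAP*

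**What the plan says.** The Power analysis section sets out its method: "The power analysis for the proposed study uses a T-test to determine differences and assumes an alpha level of 0.05", with power of 0.80 or more regarded as acceptable. On variability it says that "an SD for between-group differences in weight change of 2.8 kg was utilized". It then gives one result, 0.80, for both within-type comparisons, in a sentence that begins "To detect a 2.0 kg difference in weight change between either A vs. B or C vs. D, this study would have a power of". For Hypothesis 1 (A and D against B and C) it claims power above 0.95.

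Table 1, in the Background section, plans 52 participants in each of cells A and B and 25 in each of cells C and D, 154 in all. Its caption warns that "The total number per group is an estimate" and that cells will not be closed to reach those numbers.

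The Data analytic plan states that "Hypothesis 2 will analyze the fat responders and carbohydrate responders separately", with H2a comparing A with B and H2b comparing D with C. Both are worded directionally. The a priori comparisons each use alpha 0.05. No section says whether the tests are one- or two-sided.

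**The concern.** Power depends on cell size. With the effect, SD and alpha held fixed, a comparison of 52 with 52 must be more powerful than one of 25 with 25. A single 0.80 for both pairs therefore cannot be right for both, and a reader cannot tell which pair it describes or on what sidedness.

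Two things are at stake. First, the plan does not show what each H2 test can deliver: H2a can detect a smaller difference than 2.0 kg, while H2b, if tested two-sided, falls short of the plan's own threshold. Second, H2a and H2b are a matched pair of hypotheses whose results may well be set side by side. A reader who believes that they have equal power could take a significant H2a with a non-significant H2b as a sign that genotype matters only in fat responders, when unequal cell sizes make that pattern much likelier than its reverse.

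**Working it through.** **Inputs.** From the Power analysis section: difference d = 2.0 kg, SD s = 2.8 kg, t-test, alpha 0.05. From Table 1: n = 52 per cell (A, B) and n = 25 per cell (C, D). Two assumptions are mine: the 2.8 kg is the common within-group SD of weight change, and there is no dropout (the section gives no rate). Because sidedness is not stated, both versions are shown.

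**Formula.** Two-sample t-test with equal cells: noncentrality λ = d / (s × √(2/n)), degrees of freedom 2n − 2, power from the noncentral t distribution.

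**Reproducing the plan's figures.**

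| Comparison | n per side | λ | df | Two-sided | One-sided | Plan states |
|---|---|---|---|---|---|---|
| C vs. D | 25 | 2.0 / (2.8 × 0.2828) = 2.525 | 48 | 0.697 | 0.801 | 0.80 |
| A vs. B | 52 | 2.0 / (2.8 × 0.1961) = 3.642 | 102 | 0.950 | 0.976 | 0.80 |
| H1, A+D vs. B+C | 52 + 25 = 77 | 2.0 / (2.8 × 0.1612) = 4.432 | 152 | 0.993 | 0.997 | over 0.95 |

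The 0.80 is reproduced only for C vs. D, one-sided. A normal approximation gives the same picture: A vs. B 0.954 two-sided and 0.977 one-sided; C vs. D 0.714 and 0.811. The smallest cell size giving 0.80 with the t-test is 25 one-sided and 32 two-sided. The H1 claim holds.

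**Difference detectable with power 0.80 (SD 2.8 kg).**

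| Comparison | Two-sided | One-sided |
|---|---|---|
| A vs. B, 52 per cell | 1.55 kg | 1.37 kg |
| C vs. D, 25 per cell | 2.26 kg | 2.00 kg |

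**Could other inputs bring A vs. B down to 0.80?**
- SD: it would have to be 3.61 kg two-sided or 4.07 kg one-sided. The section cites values from 2.1 to 3.3 kg; at 3.3 kg A vs. B still has 0.865 two-sided.
- Dropout: about 40% of each cell would have to be lost (0.793 two-sided).
- Cell sizes: if the two responder types enrolled equally, as the equal-thirds estimate in the Inclusion Criteria might suggest, there would be 154 / 4 ≈ 38 per cell. Then λ = 2.0 / (2.8 × 0.2294) = 3.113 and both pairs have 0.867 two-sided or 0.925 one-sided. The powers become equal, but not at 0.80.

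**Chance of a split result when the true effect is the same in both types.** The two tests use different participants, so I treat them as independent and multiply. The second effect size is the one implied by the section's expectation that B and C lose about half of 5.1 kg: 5.1 / 2 = 2.55 kg. At 2.55 kg, A vs. B has power 0.996 two-sided (0.9985 one-sided) and C vs. D 0.884 (0.937).

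| True effect in both types | H2a significant, H2b not | H2b significant, H2a not |
|---|---|---|
| 2.0 kg, two-sided | 0.950 × (1 − 0.697) = 0.29 | (1 − 0.950) × 0.697 = 0.03 |
| 2.0 kg, one-sided | 0.976 × (1 − 0.801) = 0.19 | (1 − 0.976) × 0.801 = 0.02 |
| 2.55 kg, two-sided | 0.996 × (1 − 0.884) = 0.12 | below 0.01 |
| 2.55 kg, one-sided | 0.9985 × (1 − 0.937) = 0.06 | below 0.01 |

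Equal power of 0.80, as printed, would imply 0.80 × 0.20 = 0.16 in each direction.

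**The case against.** The strongest defence is that 0.80 is a floor. The section regards 0.80 or more as acceptable, the hypotheses are directional, and the smaller pair gives 0.801 one-sided, so the sentence could mean that whichever pair is taken has at least that much power. This is probably how the figure arose, but it does not rescue the text. Nothing says that 0.80 is a minimum, whereas the H1 claim in the same paragraph is worded as one. The floor also fails for C vs. D if the test is two-sided, and the plan does not rule that out.

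Other points for the sponsor stand. The A vs. B error is conservative and changes neither the sample size nor the conduct of the trial. Table 1 prints the unequal cells openly and calls them estimates, so both the 0.95 and the inequality depend on enrolment turning out as planned.

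A reader might infer more than the documents support. One such inference is that the trial will wrongly conclude that only fat responders benefit. The plan proposes no comparison of H2a with H2b and no such conclusion, and the risk of a split result shrinks from 0.29 at 2.0 kg to 0.12 at about 2.55 kg (two-sided). Another is that the whole power analysis fails or that H2a is underpowered. In fact H1 is sound and H2a has more power than stated.

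**Conclusion.** The joint sentence is wrong as written. At the planned cell sizes the two H2 tests do not share a power: two-sided they have 0.95 (A vs. B) and 0.70 (C vs. D), one-sided 0.98 and 0.80. For H2a the stated figure is 15 to 18 percentage points too low, which is harmless to the design. For H2b it is either a one-sided figure not labelled as such or, if the test is two-sided, about 10 points too high and below the plan's threshold. This second half matters more.

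These numbers rest on SD 2.8 kg, no dropout and the Table 1 estimates. That 0.80 does not describe A vs. B survives either sidedness, every SD the plan cites and an equal split; that the two tests differ in power holds only while the cells are unequal. The consequence for interpretation is a caution, not a flaw in the planned tests: at these sizes a significant H2a with a non-significant H2b is not, by itself, evidence that the responder types differ.

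**What to change.** State whether the H2 tests are one- or two-sided, and replace the joint sentence with one statement per pair on that basis:

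- A vs. B (about 52 per cell): power 0.95 two-sided (0.98 one-sided) at 2.0 kg; power 0.80 at about 1.55 kg (1.37 kg).
- C vs. D (about 25 per cell): power 0.70 two-sided (0.80 one-sided) at 2.0 kg; power 0.80 at about 2.26 kg (2.00 kg).

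Note beside these that the cell sizes are estimates, and that about 38 per cell would give about 0.87 two-sided or 0.93 one-sided for both pairs. In the Data analytic plan, add that H2b is the weaker test at the planned sizes, that a split result is not by itself evidence of a difference between responder types, and that both H2 estimates will be reported with confidence intervals.

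The cost is a few sentences, with no new data or procedures. The one real downside is that, if the tests are two-sided, the plan must print a C vs. D power below its own 0.80 threshold. No added enrolment is proposed.
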